9.2. Sample size

The DOD cohort of the PMA consisted of 137 DOD subjects. The sample size is fixed, based on the number of subjects enrolled in the European Cohort Study. Of the 137 DOD subjects included in the PMA Cohort, one died and one was revised by the 3-year follow-up interval. Thus, a total of 135 subjects are eligible for this PAS study and all attempts will be made to continue follow-up on all subjects throughout 10 years, including telephone follow-up for determination of device survival or revision status in cases where subjects fail to return for follow-up visits.

Smith & Nephew - Advanced Surgical Devices Division

Post-Approval Study of the R3 Biolox delta Ceramic Acetabular System – Europe	Protocol Number: R3H01/02/01/2017/Version2.0
	PMA Number P150030
	ADDENDUM Page: 20 of 25

10. ETHICAL CONSIDERATIONS

10.1. Ethical Approval

All participating sites have written EC approval to conduct the European Post-market study at their sites.

10.2. Protocol Amendments

Neither the Investigator nor the Sponsor will modify this protocol without mutual agreement. After agreement to initiate the modification - in the form of a protocol amendment - the Investigator agrees not to implement this modification until instructed to do so by the Sponsor. It will be necessary to obtain FDA and EC approval prior to implementation of any change in the protocol that may affect the scientific soundness or the rights, safety, or welfare of the subjects involved. Notification shall be submitted to the EC of the study site by the Investigator.

10.3. Informed Consent

All study subjects have already signed an EC approved ICF according to 2011:ISO14155 guidelines, GCP guidelines and all applicable national regulations. No additional consenting is required.

10.4. Risk – Benefit Analysis

A. Study Related Risks

Possible risks that may occur as a result of long term follow-up study participation are:

- Subjects will be asked to return to their doctor for follow-up visits at 5, 7 and 10 years and undergo an evaluation to assess their pain and function; however, these are not interventional procedures and are not expected to add significant time to any appointments.
- This study involves the use of x-ray evaluation. X-ray exposure is cumulative over a lifetime and total exposure should be kept to a minimum. However, if the x-ray exposure when participating in the study is equivalent to the exposure the subject would receive if they chose not to participate in the study, there is no additional risk associated with this study.
- As a result of participating in the study there could be a risk of loss of protected subject information confidentiality. All applicable confidentiality standards and data protection and privacy laws will be followed by the Sponsor to ensure that data collected is handled in confidence. Data will be coded and handled only by appropriately qualified and authorized personnel.

B. Study Related Benefits

Smith & Nephew - Advanced Surgical Devices Division

Post-Approval Study of the R3 Biolox delta Ceramic Acetabular System – Europe	Protocol Number: R3H01/02/01/2017/Version2.0 PMA Number P150030 ADDENDUM Page: 21 of 25
--	---

Because the surgery and all the follow-up visits are the same as when the subject would not participate in this study, there are no additional medical benefits associated by participating in this study. The information gained from this study may help improve the treatment of people that need to undergo total hip replacement.

Smith & Nephew - Advanced Surgical Devices Division

Post-Approval Study of the R3 Biolox delta Ceramic Acetabular System – Europe	Protocol Number: R3H01/02/01/2017/Version2.0
	PMA Number P150030
	ADDENDUM Page: 22 of 25

11. MONITORING PROCEDURES

11.1. Source Documentation

Investigators are responsible for obtaining and maintaining complete subject health information in the medical record for each subject (source documents). Examples of source documents are: hospital records, clinic and office charts, x-rays, and research subject files.

11.2. Direct Access

This study may be monitored by the Sponsor or a qualified person designated by the Sponsor. This qualified person could be an employee of the Sponsor or of a contract research organization (Sponsor's agent).

The investigator will provide Sponsor, Sponsor's agents, EC and regulatory agencies with direct access to all source data/documents to permit study-related monitoring, audits, EC review, and regulatory inspections.

11.3. Interim Monitoring Visits

A clinical monitor, whether an employee of the Sponsor or its designee, has the obligation to follow this study closely. In doing so, the monitor will, in addition to maintaining necessary contact with the study site, visit the study sites at periodic intervals according to a schedule determined by the Sponsor.

11.4. Sponsor Audits and Regulatory Inspection

Quality assurance auditors, whether an employee of the Sponsor or its designee, may evaluate study conduct at the study sites. These parties must have access to any and all study reports and source documentation, regardless of location and format.

11.5. Closeout Visit

A study close out visit will be performed by the Sponsor or designee to retrieve and account for all remaining clinical data and to resolve outstanding queries, and review regulatory requirements regarding records retention and EC reporting requirements.

11.6. Documentation of Monitoring Visits

Activities associated with a monitoring visit will be documented by the monitor.

11.7. Data Handling and Record Keeping Requirements

Case report forms (CRFs) have been supplied by the Sponsor. Subjects will be identified by a study number and subject identification code. Only the Investigator site will have the key to identify individual subjects.

The Investigator is responsible for the timely and accurate completion of CRFs. All documents related to the study must be securely archived at the study site or in a central archive.

Smith & Nephew - Advanced Surgical Devices Division

Post-Approval Study of the R3 Biolox delta Ceramic Acetabular System – Europe	Protocol Number: R3H01/02/01/2017/Version2.0
	PMA Number P150030
	ADDENDUM Page: 23 of 25

Data required according to this protocol are to be recorded on the case report forms (CRFs) at the time of the scheduled visits. Once a subject is enrolled, completed CRFs should be sent to the Sponsor, either by fax or by e-mail, as soon as possible, and no later than 10 working days upon completion of the CRFs.

11.8. Data Recording and Record Retention

Clinical research records shall be stored in a manner that ensures privacy, confidentiality, security and accessibility of the records both during and after the conduct of the study. The Investigator/Institution will take measures to prevent accidental or premature destruction of those documents. The investigator must retain essential study documents for at least 2 years after the latest of the following: the date the study is terminated or completed or the date the documents are no longer needed to support a premarket approval application. If the Investigator needs to dispose of the documents, the Sponsor should be contacted for approval prior to disposal or destruction. The investigator will retain these documents for a longer period if required by the applicable local laws. If the responsible investigator retires, relocates, or withdraws from responsibility of keeping the study records, custody must be transferred to a person who will accept the responsibility. The Sponsor must be notified in writing of the name and address of the new custodian. Under no circumstance shall the Investigator relocate or dispose of any study documents before having obtained written approval from the Sponsor.

Smith & Nephew - Advanced Surgical Devices Division

Post-Approval Study of the R3 Biolox delta Ceramic Acetabular System – Europe	Protocol Number: R3H01/02/01/2017/Version2.0
	PMA Number P150030
	ADDENDUM Page: 24 of 25

12. DEVIATIONS FROM PROTOCOL

A protocol deviation is an instance of failure, intentionally or unintentionally, to follow the requirements of the protocol. Protocol deviations include but are not limited to: endpoint variable criteria, study visits outside the window or missed.

12.1. Protocol Deviation Reporting Requirements

Deviations must be reported to the Sponsor as soon as reasonably possible. When protocol deviations affect the scientific soundness of the study, or the rights, safety or welfare of the study subjects, the Investigator must also report protocol deviations to the EC of the study site.

Investigators and all study staff (staff at site and at Sponsor) are responsible for ensuring adherence to study protocol. During the monitoring visits, the Sponsor representative will review all deviations with the Investigator. If a deviation is discovered outside of a monitoring visit, it should be evaluated via phone, email or letter. Appropriate measures to address the occurrence, additional monitoring visits, or audit of the study should be taken, which may include defining and implementing a Corrective and Preventive Action (CAPA).

13. Reports

Annual reports will be prepared and submitted to the ECs in accordance with on-going approval requirements.

It is expected that it will take 7 more years to complete data collection for all subjects at the 10-year follow-up interval. Once all of the study data is collected and the database is closed for analysis, it is anticipated that the data analysis and the preparation of a final PAS study report will take three (3) months to complete.

The sponsor will submit reports to the US FDA every 6 months for the first two years of the study, and then annually to completion.

Smith & Nephew - Advanced Surgical Devices Division

Post-Approval Study of the R3 Biolox delta Ceramic Acetabular System – Europe	Protocol Number: R3H01/02/01/2017/Version2.0
	PMA Number P150030
	ADDENDUM Page: 25 of 25

14. Publication policy

14.1. Multicenter Publication

The sponsor may invite the investigator to participate in a multicenter publication of the study results, in which case it will be ensured that the documents submitted for publication comply with the publisher's requirements for authors and contributors. If the publisher has no such requirements, it will be ensured that the publication meets the authorship and contributorship requirements as stated in the current Smith & Nephew Global Policy and Procedure relating Scientific Disclosures. Also, the sponsor will select a publisher based on mutual agreement with the investigators, who are invited to participate in the publication.

14.2. Investigator Publication

The investigator may publish his/her own data subject to the following restrictions:

- the multicenter manuscript must be published prior to investigators publishing their own data;
- the manuscript shall be submitted to the Sponsor for review prior to submitting the manuscript for publication;
- the manuscript must reference the study multicenter manuscript.

14.3. Authorship

The sponsor may invite the investigator to participate in a multicenter publication of the study results. The sponsor will select a publisher based on mutual agreement with the investigators who are invited to participate in the publication. Unless otherwise required by the journal of publication or the forum in which a presentation is made, authorship will comply with ICMJE current Uniform Requirements for Manuscripts Submitted to Biomedical Journals: Writing and Editing for Biomedical Publication. ICMJE recommends that authorship be based on the following criteria:

- Substantial contributions to the conception or design of the work; or the acquisition, analysis, or interpretation of data for the work; and
- Drafting the work or revising it critically for important intellectual content; and
- Final approval of the version to be published; and
- Agreement to be accountable for all aspects of the work in ensuring that questions related to the accuracy or integrity of any part of the work are appropriately investigated and resolved.
- In addition to being accountable for the parts of the work he or she has done, an author should be able to identify which co-authors are responsible for specific other parts of the work. In addition, authors should have confidence in the integrity of the contributions of their co-authors.

Subject to a publisher's copyright, Site and/or Investigator will own the copyright on publications and other copyrightable material produced as a result of the Study.

1 LIST OF ABBREVIATIONS

Abbreviation	Definition
ADE	Adverse Device Effect
ADL	Activity limitations daily living
AE	Adverse Event(s)
ASADE	Anticipated Serious Adverse Device Effect
CI	Confidence Interval
CRF	Case Report Form
DC	Discharge
DevD	Device Deficiency(ies)
FAS	Full Analysis Set
FU	Follow-Up
HHS	Harris Hip Score
HOOS	Hip Disability and Osteoarthritic Outcome Score
ISO	International Organization for Standardisation
LSLV	Last Subject Last Visit
MAR	Missing at Random
MMRM	Mixed Model Repeated Measure
N/A	Not Applicable
NICE	National Institute for Clinical Excellence
ODEP	Orthopaedic Data Evaluation Panel
OP	Operative
PP	Per-protocol Population

CONFIDENTIAL AND PROPRIETARY

This document contains information that is confidential and proprietary to Smith & Nephew PLC and Smith & Nephew, Inc. and is intended for use only by Smith+Nephew and its manufacturer. It shall not be reproduced or copied in whole or in part, nor shall the contents be disclosed by any means without prior written permission from Smith+Nephew, nor shall anyone make any use of it that is contrary to the expressed or implied wishes of Smith+Nephew.

Statistical Analysis Plan

A prospective, multicenter, non-randomized, clinical outcomes study of the R3[◊] Acetabular System in patients with degenerative hip disease

Number:
R3H01/02/01/2017
ST: 1103
Version: 3.0
Page: 5 of 18

Abbreviation	Definition
QoL	Quality of Life
SADE	Serious Adverse Device Effect
SAE	Serious Adverse Event
SAF	Safety Analysis Set
SAP	Statistical Analysis Plan
TFL	Tables, Figures and Listing
UCLA	University of California, Los Angeles
USADE	Unanticipated Serious Adverse Device Effect
VAS	Visual Analogue Scale

CONFIDENTIAL AND PROPRIETARY

This document contains information that is confidential and proprietary to Smith & Nephew PLC and Smith & Nephew, Inc. and is intended for use only by Smith+Nephew and its manufacturer. It shall not be reproduced or copied in whole or in part, nor shall the contents be disclosed by any means without prior written permission from Smith+Nephew, nor shall anyone make any use of it that is contrary to the expressed or implied wishes of Smith+Nephew.

Statistical Analysis Plan

A prospective, multicenter, non-randomized, clinical outcomes study of the R3[◊] Acetabular System in patients with degenerative hip disease

Number:
R3H01/02/01/2017
ST: 1103
Version: 3.0
Page: 6 of 18

2 INTRODUCTION

The following Statistical Analysis Plan (SAP) details the statistical considerations, including the data analysis methods, for the Study Protocol R3H01/02/01/2017 version 2.0/BNA. Related documents to this SAP are the Study Protocol, Case Report Form (CRF), and Table, Figure and Listing (TFL) Template Shells. This SAP is also an amendment to the previous finalized versions 1.0 and 2.0.

3 STUDY DESIGN

This is a multicenter prospective observational post-market clinical follow-up study that includes 512 patients who had a total hip replacement with the R3 Acetabular System and either cemented or cementless hip stem. The schedule of events is provided in Table 1.

Table 1. Study schedule of events

Study Activity	Preop	Op	DC	3M (+/- 14d)	1Y (+/- 2m)	3Y (+/- 3m)	5Y (+/- 6m)	7Y (+/- 6m)	10Y (+/- 6m)
Inclusion/Exclusion	X								
Informed Consent	X								
Demographics/Med History		X							
Harris Hip Score	X			X	X	X	X	X	X
UCLA	X			X	X	X	X	X	X
HOOS	X			X	X	X	X	X	X
Radiograph Evaluation			X		X*	X	X	X	X
Operative		X							
Discharge			X						
Adverse Events		X	X	X	X	X	X	X	X

* Full pelvic overview

4 STUDY OBJECTIVES

The objective of this study is to determine the long-term safety and effectiveness of the R3 Acetabular System by analysing the clinical, radiographic responses and the adverse event rates for

CONFIDENTIAL AND PROPRIETARY

This document contains information that is confidential and proprietary to Smith & Nephew PLC and Smith & Nephew, Inc. and is intended for use only by Smith+Nephew and its manufacturer. It shall not be reproduced or copied in whole or in part, nor shall the contents be disclosed by any means without prior written permission from Smith+Nephew, nor shall anyone make any use of it that is contrary to the expressed or implied wishes of Smith+Nephew.

Statistical Analysis Plan

A prospective, multicenter, non-randomized, clinical outcomes study of the R3[◊] Acetabular System in patients with degenerative hip disease

Number:
R3H01/02/01/2017
ST: 1103
Version: 3.0
Page: 7 of 18

patients undergoing primary total hip arthroplasty using the R3 Hip System (R3 Acetabular System). The study hypothesis is as follows: implant survivorship (Kaplan-Meier) (revision for any reason) of the R3 cup is at least 97% at 3 years, 95% at 5 years, 93% at 7 years, and 90% at 10 years follow-up.

5 STUDY ENDPOINTS

5.1 Primary Endpoint

The primary endpoint is implant survivorship at 10 years postoperatively.

5.2 Secondary Endpoint

Secondary endpoints include the following:

- ▲ Implant survivorship of the acetabular/cup at 10 years postoperatively
- Modified Harris Hip Score (mHHS)
- Hip disability and Osteoarthritis Outcome Score (HOOS)
- University of California, Los Angeles (UCLA) Rating
- Radiographic evaluation
- Patient Satisfaction

5.3 Safety Endpoints

The safety endpoints are as follows:

- Incidence of Adverse Events by International Organization for Standardization (ISO) classifications
- Incidence of AEs by severity,
- Incidence of AEs by relationship to study device,
- Incidence of serious adverse events (SAEs),
- Incidence of Serious Adverse Device Effects (SADEs),
- Incidence of Unanticipated Serious Adverse Device Effects (USADEs),
- Incidence of Anticipated Serious Adverse Device Effects (ASADEs),
- Incidence of procedure-and or device related events,

CONFIDENTIAL AND PROPRIETARY

This document contains information that is confidential and proprietary to Smith & Nephew PLC and Smith & Nephew, Inc. and is intended for use only by Smith+Nephew and its manufacturer. It shall not be reproduced or copied in whole or in part, nor shall the contents be disclosed by any means without prior written permission from Smith+Nephew, nor shall anyone make any use of it that is contrary to the expressed or implied wishes of Smith+Nephew.

Statistical Analysis Plan

A prospective, multicenter, non-randomized, clinical outcomes study of the R3[◊] Acetabular System in patients with degenerative hip disease

Number:
R3H01/02/01/2017
ST: 1103
Version: 3.0
Page: 8 of 18

- Listing of revisions and components revised.

6 STATISTICAL CONSIDERATIONS

6.1 Determination of Sample Size

The target enrollment during this study was 500 patients however 512 subjects have been enrolled. This number of patients leads to representative results with a greater precision of the survival rates, i.e. small confidence intervals.

The sample size is large enough to satisfy pseudo-regulatory requirements set-forth in individual European countries such as the Orthopaedic Data Evaluation Panel¹ (ODEP) and the National Institute for Clinical Excellence (NICE) requirements². According to the ODEP criteria for categorizing products in relation to NICE's long-term benchmarks for hip replacements, a level A study (strongest evidence) requires an initial cohort of 500 patients or more.

6.2 Randomisation

Not applicable.

6.3 Interim Analysis

Not applicable as LSLV has been performed.

7 STATISTICAL ANALYSIS

7.1 General

Smith+Nephew's Global Biostatistics group will conduct the statistical analysis for this study. Unless otherwise stated, all significance tests and hypothesis testing will be two-sided, performed at the 5% significance level. Resulting p-values will be quoted and 95% two-sided confidence intervals will be generated where appropriate. All p-values will be rounded to three decimal places, p-values less than 0.001 will be presented as '<0.001' in all tables.

CONFIDENTIAL AND PROPRIETARY

This document contains information that is confidential and proprietary to Smith & Nephew PLC and Smith & Nephew, Inc. and is intended for use only by Smith+Nephew and its manufacturer. It shall not be reproduced or copied in whole or in part, nor shall the contents be disclosed by any means without prior written permission from Smith+Nephew, nor shall anyone make any use of it that is contrary to the expressed or implied wishes of Smith+Nephew.

Statistical Analysis Plan

A prospective, multicenter, non-randomized, clinical outcomes study of the R3[◊] Acetabular System in patients with degenerative hip disease

Number:
R3H01/02/01/2017
ST: 1103
Version: 3.0
Page: 9 of 18

Where data summaries are specified, categorical and ordinal variables will be summarized with frequencies and percentages. Continuous variables will be summarized with the following summary statistics: number of observations, mean, median, standard deviation, minimum and maximum values. All analyses will be performed in SAS 9.4 (or later).

7.2 Analysis Populations

The following are the analysis populations used in summarizing all tables:

Safety Analysis Population (SAF)

This will include all subjects (Hips) enrolled and implanted with the study device in the study.

Full Analysis Set (FAS)

The FAS population will include all subjects (Hips) in the SAF with at least one postoperative assessment on any of the Patient Reported Outcome Measures (PROMs).

Per Protocol (PP) Population

The PP population will include all subjects (Hips) in FAS, who have no significant protocol deviations and satisfy all study eligibility criteria and the inclusion/exclusion criteria. Significant protocol deviations leading to removal from the PP population will be determined and finalized prior to the final analyses at 10 years. The final assignment of a subject to the PP population will be established after all protocol deviations have been reviewed and evaluated. Subjects excluded from the PP will be documented/listed together with their reason(s) for exclusion.

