7.9 Analysis of Primary Endpoint

The Kaplan-Meier survival estimate would be used to estimate implant survivorship. Time to device revision will be the endpoint of interest to estimate the implant survivorship. Implant survival time (in months) is computed as: (Event Date – Operative Date+1)/30.4375.

Implanted hips that continue until study completion without an on-study revision will be censored at their last known date of participation in the study. Any premature hip discontinuation from study due to a subject's death or any other reason will be censored on the date of this discontinuation. A subject who is lost to follow-up will be censored at the subject's last known contact date. The Cumulative proportion of implant survivorship at 36 months (3-year), 60 months (5 years), 84 months (7 years) and 120 months (10 years) will be estimated and displayed accordingly. These Kaplan-Meier estimates will be provided with their corresponding two-sided 95% Confidence Intervals (CIs). If feasible, Kaplan-Meier survival graphs will be displayed to graphically illustrate implant survivorship over the study duration.

For the a-priori protocol-specified hypothesis, if the lower bound of 95% two-sided CIs at 3 years, 5 years, 7 years and 10 years are not less than 97%, 95%, 93% and 90% respectively, then we conclude that implant survivorship of the R3 cup is at least 97% at 3 years, 95% at 5 years, 93% at 7 years, and 90% at 10 years follow-up respectively.

The primary endpoint analysis will be performed on the FAS population. As sensitivity analysis, the same analysis will be performed on the PP population.

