7.10 Analysis of Secondary Endpoints

- HOOS sub-scores, HHS (and its subscores) and UCLA would be summarized using descriptive summary characteristics for continuous variables at the preoperative and all postoperative time points. Changes from the preoperative (baseline) to subsequent postoperative visit(s) would also be summarized using descriptive statistics for continuous

CONFIDENTIAL AND PROPRIETARY

This document contains information that is confidential and proprietary to Smith & Nephew PLC and Smith & Nephew, Inc. and is intended for use only by Smith+Nephew and its manufacturer. It shall not be reproduced or copied in whole or in part, nor shall the contents be disclosed by any means without prior written permission from Smith+Nephew, nor shall anyone make any use of it that is contrary to the expressed or implied wishes of Smith+Nephew.

Statistical Analysis Plan

A prospective, multicenter, non-randomized, clinical outcomes study of the R3[◊] Acetabular System in patients with degenerative hip disease

Number:
R3H01/02/01/2017
ST: 1103
Version: 3.0
Page: 16 of 18

variables. Mixed Model Repeated Measures (MMRM) with a missing at random (MAR) assumption to account for the pattern of missing longitudinal data would be used to analyze the Patient Reported Outcome Measures (PROMs) to compare the scores between the preoperative and postoperative visit time points. The model will include fixed effect term for visit. The Kenward Rogers denominator degrees of freedom would be used coupled with a specification for an unstructured covariance matrix. The test of any of the comparisons between the preoperative and postoperative visits will be concluded to be statistically significant if $p < 0.05$. Model-based Means or Least Square (LS) Means for all visits as well as the differences between each postoperative versus the preoperative visit and their 95% two-sided Confidence Intervals (CI) would be presented. Should greater than 10% of any of the PROMs data on at least at two of the postoperative timepoints be missing, MMRM would not be used.

- For radiographic findings, patient satisfaction and Trendelenburg, descriptive summary statistics for categorical variables such as frequency (n) and percentage (%) will be presented by visit.

The secondary endpoint analysis will be performed only on the FAS population.

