7.11 Analysis of Safety Endpoints

An overall summary AE table that would summarize as number (n) and percentages (%), the overall incidence according to subjects (and hips) with at least one AE; subjects (and hips) with at least one AE by worst severity (mild, moderate, or severe), by worst outcome (resolved, ongoing/unresolved, death or removal/revision of components), worse relatedness to device, SAEs, ADEs, SADEs, ASADEs and, USADEs. Classification of AEs would also be summarized using ISO classifications. A data listing with all AEs (and their classifications) reported on-study will be presented. Finally, the incidence of device-and/or procedure related AE by their type will be presented too.

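### The SAP analyses by hip without linking the two hips of one patient; if bilateral patients are analysed this way, survivorship intervals are slightly too narrow and patient-level scores are double-weighted

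*SAP*

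**What the plan says.** SAP 7.2 uses the hip throughout. The safety population reads "This will include all subjects (Hips) enrolled and implanted with the study device in the study". The next set down reads "The FAS population will include all subjects (Hips) in the SAF with at least one postoperative assessment on any of the Patient Reported Outcome Measures", and the per-protocol set is drawn from it in the same terms.

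SAP 7.9 follows individual hips: "Implanted hips that continue until study completion without an on-study revision will be censored at their last known date of participation in the study". It then draws the primary conclusion from the interval: "if the lower bound of 95% two-sided CIs at 3 years, 5 years, 7 years and 10 years are not less than 97%, 95%, 93%", with 90% as the 10-year limit. No variance estimator, transformation or clustering is named.

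SAP 7.10 analyses the scores with an MMRM that has visit as its only fixed effect, "coupled with a specification for an unstructured covariance matrix". It does not say whether the block is the patient or the hip.

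The SAP does expect subjects and hips to differ. Section 7.6 counts subjects presenting and hips expected separately, and 7.11 gives "the overall incidence according to subjects (and hips) with at least one AE". The eligibility criteria (Protocol 5.1 and 5.2) do not rule out a second study hip. Neither document states how a patient with two study hips is handled.

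**The concern.** A standard Kaplan-Meier interval treats its rows as independent. Two hips in one patient share the patient's age, activity, bone quality and infection risk, and often the surgeon. If their outcomes are positively correlated, an interval computed by hip is too short. The primary conclusion is read from the lower bound, so the error favours passing.

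UCLA activity and patient satisfaction describe the person rather than the joint. If the hip is the data row, a bilateral patient enters these summaries twice with nearly the same value. That inflates n, distorts means and percentages towards bilateral patients, and shortens any model-based interval.

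**Working it through.** **Inputs from the documents.** N = 512, called patients in SAP 3 and subjects in SAP 6.1; no hip count is given. Limits of 97, 95, 93 and 90% at 3, 5, 7 and 10 years, and two-sided 95% intervals (SAP 7.9).

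**Assumptions.** Bilateral share of patients b = 5-20%. Within-patient correlation rho = 0.1-0.3 for revision, and rho = 1 as the extreme for a score entered identically for both hips. No censoring. Because 7.9 names no transformation, linear and log-log intervals are both shown.

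**Step 1, baseline.** The plan has no precision figure to reproduce; SAP 6.1 refers only to small intervals. For 512 independent units at 90% survivorship, the half-width is 1.96 x sqrt(0.90 x 0.10 / 512) = 2.60 percentage points.

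**Step 2, share of hips.** The share of hips that come from bilateral patients is f = 2b/(1 + b):
- b = 5%: 0.10/1.05 = 0.095
- b = 20%: 0.40/1.20 = 0.333

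So 5-20% of patients supply 9.5-33% of the rows, which is the double weighting. For clusters of one or two hips, the design effect is D = 1 + f x rho.

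**Step 3, survivorship.** D runs from 1 + 0.095 x 0.1 = 1.01 to 1 + 0.333 x 0.3 = 1.10. At D = 1.10 the interval should be sqrt(1.10) = 1.049 times as wide, so 2.60 becomes 2.73 points. Coverage of the nominal 95% interval is then about 93.8%. A simulation of 20,000 data sets at the same design effect (20% of hips from bilateral patients, rho = 0.5) gave a variance ratio of 1.10 and coverage of 93.5%.

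**Step 4, the decision rule.** With S = 1 - k/512 and SE = sqrt(D x S(1 - S)/512), the lower bounds are:
- linear: S - 1.96 x SE
- log-log: exp(-exp(ln(-ln S) + 1.96 x SE/(S x |ln S|)))

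The largest number of revisions k that still passes is:

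| Interval | D | 3 y | 5 y | 7 y | 10 y |
|---|---|---|---|---|---|
| log-log | 1.00 | 7 | 15 | 24 | 37 |
| log-log | 1.10 | 7 | 15 | 23 | 37 |
| linear | 1.00 | 9 | 17 | 26 | 39 |
| linear | 1.10 | 9 | 17 | 25 | 38 |

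On the log-log scale only the 7-year limit moves: with 24 revisions the lower bound falls from 93.09% to 92.96%. At 10 years, 37 revisions still pass, with the bound falling from 90.16% to 90.02%.

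If 512 is the number of patients, the hips number 512 x 1.05 = 538 to 512 x 1.20 = 614. The 10-year log-log limit without clustering is then 40-46 rather than 37. Repeating the comparison with 538 and 614 hips again moves no limit by more than one revision.

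**Step 5, a patient-level score entered twice (rho = 1).** D = 1.095 to 1.333, reported as 1.10-1.33. The correct standard error is sqrt(D) = 1.047 to 1.155 times the reported one. The reported one is therefore too small by 1 - 1/1.047 = 4% to 1 - 1/1.155 = 13%.

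**The case against.** The strongest reply is that the documents never say that any patient has two study hips. With none, nothing changes. That is correct, and it makes every consequence here conditional.

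A reader might infer three stronger statements that the documents do not support.

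- **That the reported intervals are known to be too narrow.** This needs a bilateral count and a positive correlation, and neither is given.
- **That the MMRM treats a patient's hips as independent and UCLA is entered twice by rule.** SAP 7.10 does not name the block, which could be the patient. Double entry follows only if the hip is the row, which the population wording suggests but does not state.
- **That the score intervals are wrong by the full 4-13%.** Correlation of 1 needs both hips to share a baseline and visit dates. Staged operations give each hip its own baseline and follow-up clock, which lowers the correlation.

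Two further limits stand. SAP 7.10 drops the MMRM if more than 10% of scores are missing at two or more postoperative visits, which is possible over ten years. Satisfaction is only tabulated. In those cases there is no model-based interval to correct, and only the double weighting in the descriptive tables remains. In addition, the scores carry no success limit, so no pass-or-fail conclusion depends on them.

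The reply does not remove the core point. The primary interval is specified by hip, the SAP elsewhere expects hips and subjects to differ, and no method allows for the pairing.

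**Conclusion.** The gap is real and minor. It goes beyond missing detail, because the hip-level interval as specified feeds the lower-bound rule and a better interval is readily available. Under the assumed ranges, survivorship intervals should be at most about 5% wider, and no pass limit moves by more than one revision. The clearer consequence is for patient-level scores, where bilateral patients count twice if the hip is the row.

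The size rests on the assumed bilateral share and correlations, on no censoring, and on an interval type that the SAP leaves open. It would be wrong to conclude that the survivorship claim is in doubt for this reason: only a result within one revision of a limit could be affected.

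**What to change.** 1. Report the numbers of patients, hips and bilateral patients. SAP 6.3 says that the last subject's last visit has taken place, so the sponsor can count them now. If no patient is bilateral, one sentence closes the point.
2. In 7.9, compute the Kaplan-Meier interval with the subject as cluster, by a robust variance or a subject-level bootstrap.
3. In 7.10, name the MMRM block. For mHHS and HOOS, use subject-clustered standard errors, or a subject-level term where it can be estimated.
4. Count UCLA and patient satisfaction once per subject per visit, in the descriptive tables as well as in any model.

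The cost is SAP wording and a little code, with no new data. The drawbacks are slightly wider intervals and, if few patients are bilateral, a subject-level term that may be poorly estimated; clustered standard errors are then the simpler choice.
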